## 6.2 Subject Exclusion Criteria

Patients will be excluded from the trial if at time of enrollment:

1. Evidence of relapsed disease by morphologic, cytogenetic or molecular diagnostic tools.
2. Hypersplenism documented by imaging study (US or CT)
3. Pregnant women
4. Patient who underwent TCD boost without counts recovery and are considered for another TCD boost will be treated off protocol.

## 7.0 RECRUITMENT PLAN

Patients who fulfill the eligibility criteria as listed in section 6.0 will be recruited for this study by an attending physician of the Adult and Pediatric BMT service. This protocol will take due notice of NIH/ADAMHA policies concerning inclusion of women and minorities in clinical research population.

## 8.0 PRETREATMENT EVALUATION

The patient will undergo comprehensive medical evaluation which will include:

1. Complete physical exam and medical history.
2. GVHD assessment
3. Infectious status assessment, including PCR studies for CMV, HHV6, EBV and adenovirus. Imaging studies if indicated.
4. Complete medications review
5. Complete blood counts (CBC) and reticulocyte count
6. Complete metabolic panel
7. Chimerism studies – bone marrow and peripheral blood lineage (T cells, B cells and Myeloid)
8. Splenic size evaluation by US or CT scan only for patients for whom it is clinically relevant
9. Anti-neutrophil antibodies, anti-platelet antibodies and Coombs test.
10. Bone marrow aspiration and biopsy including (1) complete disease evaluation for patients with hematologic malignancies and (2) cellularity evaluation for all patients

## 9.0 TREATMENT/INTERVENTION PLAN

1. CBC will be checked weekly for the first two months or until independent of G-CSF and transfusion support, then every two weeks (or more frequently if clinically indicated ) until day 100 post TCD stem cell boost. In patients who by day 100 have partial recovery, monitoring blood counts will continue every 2-4 weeks.
2. Bone marrow aspirate and biopsy for assessment of engraftment will be done approximately on day 28 (+/- 7 days) and day 100 post TCD boost (+/- 10 days) and afterwards as required per BMT guidelines.
3. Peripheral blood lymphocyte phenotyping and in-vitro response to mitogen will be assessed on day 28 and day 100 post TCD boost and afterwards as part of routine post transplant assessment until CD4 reaches 200 and PHA>100th percentile.

## 10.0 EVALUATION DURING TREATMENT/INTERVENTION

All patients will be closely monitored and evaluated as per MSKCC BMT standard of care guidelines. Study specific assessment schedule listed in table below.

Amended: 02-DEC-2015

Page 13 of 24

Procedures	Pre-treat	Days Post-Boost												
		7	14	21	28	35	42	49	56	63	70	77	84	100
Window	45	(+/-) 3	(+/-) 3	(+/-) 3	(+/-) 7	(+/-) 3	(+/-) 3	(+/-) 3	(+/-) 3	(+/-) 7	(+/-) 7	(+/-) 7	(+/-) 7	(+/-) 7
Eligibility	X													
Informed consent	X													
History/Physical	X													
CBC	X	X	X	X	X		X		X		X		X	X
Reticulocyte Count	X	X	X	X	X		X		X		X		X	X
Blood Chemistry/CMP (1)	X	X		X			X		X		X		X	X
Infection Testing (2)	X													
ECG and/or ECHO (only for new cardiac symptoms)	X													
US or CT (only if clinically indicated)	X													
Pregnancy Test (3)	X													
Creatinine Clearance	X													
Anti-Neutrophil Antibodies	X													
Coombs Test	X													
Bone marrow aspirate and biopsy (standard of care and research samples)	X					X								X
Correlative Studies – PB Research Sample (4)					X									X
Immune evaluation	X				X									X
Chimerism (Blood and BM)	X				X									X
GvHD evaluation (5)			X	X	X	X	X	X	X	X	X	X	X	X
Toxicity assessment		X	X	X	X	X	X	X	X	X	X	X	X	X

(1) BUN, creatinine, electrolytes, glucose, total protein, albumin, AST, ALT, bilirubin, alkaline phosphatase

(2) CMV, EBV, HHV-6, adeno virus by PCR

(3) Required for FCBP only

(4) Peripheral blood samples will be collected for correlative research studies

(5) GvHD assessment to begin at engraftment

## 10.1 Correlative Studies

BM aspirate will be obtained prior to administration of the TCD boost as well as on day 30 and day 100 post TCD boost. These studies will give an insight to the events at the level of the stem cells and its interaction with the bone marrow microenvironment.

These correlative studies will be performed in [name] lab, where the results will be analyzed as well. The studies will include the following:

1. To study early hematopoietic progenitors colony forming cells assays will be used. These will include: erythroid burst forming units (BFU-E), Megakaryocytes colony forming units (CFU-Meg) and granulocyte -macrophage colony forming unit (GM-CFU).
2. To study a more primitive hematopoietic progenitors the cobblestone area-forming cell (CAFC) assay will be used.

Amended: 02-DEC-2015

Page 14 of 24

3. To study the interaction between the patients BM stroma and the donor stem cells a cobblestone area-forming cell (CAFC) assay will be set from BM aspirate pre boost and an aliquot of donor stem cells will be added to the established culture.

Peripheral blood sample will be obtained on days +28, +100 post TCD boost and will be sent to the clinical immunology laboratory to assess immune reconstitution with response to administration of the TCD boost. Peripheral blood samples will also be collected on those time-points and processed at HOTB for correlative studies.

## 11.0 TOXICITIES/SIDE EFFECTS

Toxicities will be graded according to NCI CTAE version 4.0.

**Toxicities associated with stem cell infusion:** The T-cell depleted peripheral blood stem cells are infused in a small volume (approximately 10-20 ml). Possible side effects include side effects associated with blood product infusions such as: changes in blood pressure, fever, headache, shortness of breath, chills, sweats, nausea/vomiting, bad taste in the mouth. Pre-medications are given to reduce these side effects.

**Graft-versus-host-disease (GvHD):** acute and chronic GVHD may develop after allogeneic transplantation and can be disabling and fatal. CD34+ selection and CD3+ depletion reduces the number of T cells in the HPC(A) or HPC(M) graft but GVHD can occur after TCD transplant. Acute and/or chronic GVHD will be treated with immunosuppressive drugs as per transplant service guidelines.

## 12.0 CRITERIA FOR THERAPEUTIC RESPONSE/OUTCOME ASSESSMENT

Definitions of events in the study period that are important for analysis and treatment

### 1. Peripheral blood counts recovery

Peripheral blood counts recovery will be documented by CBC checks every 2 weeks. Response will be defined by stable blood counts (ANC>1000, Hb>8 with absolute reticulocyte count>20x10^9/L ,and Plt>50,000) without support of blood product transfusions and/or growth factors.

### 2. Chimerism

Chimerism will be performed by analysis of bone marrow cells as well peripheral blood cells subpopulations (T cells, B cells, neutrophils) by standard karyotype or FISH analysis for sex mismatched host-donor or short tandem repeat analysis at 1 month and at 100 days post TCD boost and afterwards at regular time points as per routine BMT guidelines.

### 3. Immunologic reconstitution

Our previous studies have identified time points at which the various immunologic functions can be expected to return. Immunophenotyping including CD4/CD8 will be performed on circulating lymphocytes of all patients as well as T cell proliferation in response to PHA at 1 month and 100 days post-TCD boost. These markers will be used to

define immune reconstitution.

#### 4. Graft versus Host Disease

Standard BMT-CTN and IBMTR systems clinical criteria as defined by Rowlings, et al. will be used to establish and grade acute GvHD. Data will be collected weekly and up to day 100 after the TCD boost to characterize the severity of symptoms and signs caused by acute GvHD and to evaluate possible confounding factors.

Real time data collection will include descriptive characteristics of rash and estimated body surface area involved, extent of dermal/epidermal separation, identification of concomitant causes of increased bilirubin other than GvHD, presence or absence of nausea, vomiting or anorexia persistent after engraftment, peak diarrhea volume with annotations concerning the presence after engraftment, peak diarrhea volume with annotations concerning the presence or absence of urinary mixing and estimates of true diarrhea volume, presence or absence of abdominal cramps, presence or absence of frank stool blood or melena, concomitant causes of GI symptoms other than GvHD, biopsy results, identification of any agents used for treatment and autopsy results.

Chronic GvHD will be diagnosed and graded according to the NIH consensus criteria.

### 13.0 CRITERIA FOR REMOVAL FROM STUDY

If at any time the patient is found to be ineligible for the protocol as designated in the section on Criteria for patient/subject eligibility, the patient will be removed from the study. Also patients may be removed from the study if requested by the patient. Management will continue as per standard allogeneic HSCT guidelines.

### 14.0 BIOSTATISTICS

This protocol investigates the efficacy of T-cell depleted boosts for poor graft function (PGF) in two cohorts of patients. The first cohort is patients who have PGF without any active infection, GVHD, and end organ compromise at the time of TCD boost administration (Cohort A). The second cohort is patients who have PGF with active infection, GVHD, or end organ compromise at the time of TCD administration (Cohort B). The protocol will have two single-arm phase II trials to investigate the efficacy separately in the two cohorts. The primary endpoint in both cohorts is the achievement of objective count recovery as defined in section 12.0 at 100 days following the intervention without the aid of growth factors. Patients who die prior to 100 days or those who achieve count recovery but lose their counts prior to 100 days will be treated as treatment failures.

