Objective improvement in counts ( $ANC > 0.5 \times 10^9/L$  without G-CSF support and  $Plt > 50 \times 10^9/L$ ) occurred in 20 patients with a median of 3.4 months (range 0.36–22.2 months) post TCD boost. In 17 out of the 20 patients there was further improvement of peripheral blood counts ( $ANC > 1.0 \times 10^9/L$  and  $Plt > 100 \times 10^9/L$ ) with median of 8.8 months. For the 20 patients who had objective improvement in counts, the median cell dose was  $1.8 \times 10^7$  SBA-E- cells/kg when bone marrow, HPC(M) was used as source of stem cells and  $6.7 \times 10^6$  CD34+ cells/kg for patients who received HPC(A) TCD boost. Among the other 8 patients who were alive post day 28 after the TCD boost and had persistent poor graft function without objective improvement in blood counts, 2 had ongoing GVHD and in the other 6 patients the lack of response was of unknown reason. The stem cell boost infusion was well tolerated in all patients and no grade 2 or higher adverse events were reported. New onset GVHD, acute or chronic, was not documented in any of the patients, however, GVHD flare was documented in 2 patients with preexisting GVHD. The 2 and 5 years survival post TCD boost were 48.6% and 37.1%, respectively. The median survival for patients who achieved minimal objective count recovery was 77.58 months and for those who achieved optimal count recovery 80.34 months as compared to 6.61 months for patients who had no peripheral blood counts recovery. The 2 years OS for patients with peripheral blood counts recovery was 90% as compared to 18% for patients without counts recovery. Patient's medical condition at time of TCD boost administration had significant impact on response to treatment and survival. The best outcomes were seen in patients with no evidence of end-organ dysfunction (defined as creatinine > 2, total bilirubin > 2, need for mechanical ventilation and active infection) and who were still outpatients. In this group of patients 56% were alive and with stable peripheral blood counts on day 100 post administration of TCD boost as oppose to the other group of patients where only 10% were alive and with stable counts.

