#### Cohort A:

A Simon's 2-stage optimal design will be used to investigate the primary endpoint in patients without active infection or end organ disease. Based on historical MSKCC data, the boost treatment strategy will be considered promising for further investigation if 65% achieve objective recovery at 100 days.

However, if 40% or fewer achieve sustained recovery, the strategy will not be considered.

promising. Based on these rates, the trial will accrue a maximum of 28 patients. In the first stage of the trial, response will be evaluated in the first 13 patients. The trial will stop due to a lack of efficacy if 5 or fewer achieve objective recovery; otherwise, an additional 15 will accrue. At the end of the trial, if at least 15 out of the 28 patients achieve an objective recovery at 100 days, the boost intervention will be considered promising for further investigation. The type I and type II errors are both set at 0.10.

The estimated accrual is 7-10 patients/year and the overall study duration is 3-4 years.

The Cohort A trial includes early termination in the event that patients have high rates of grade III-IV acute GVHD. The stopping rules below are based on a maximum of 28 patients receiving the boost intervention.

Failure Type	# of failures needed to stop the study	Failure rate in the population	Probability boundary is crossed
Acute GVHD (Grade III-IV)	3 in the first 8 patients	0.10	0.09
	4 in the first 14 patients 5 in the first 20 patients 6 in the first 27 patients 7 at any point		
		0.35	0.96

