#### Cohort B:

A Simon's 2-stage optimal design will be used to investigate the primary endpoint in patients with active infection and/or end organ disease. The boost treatment strategy will be considered promising for further investigation if 35% achieve objective recovery at 100 days. However, if 10% or fewer achieve sustained recovery, the strategy will not be considered promising. Based on these rates, the trial will accrue a maximum of 19 patients. In the first stage of the trial, response will be evaluated in the first 11 patients. The trial will stop due to a lack of efficacy if one or no patient achieves objective recovery; otherwise, an additional 8 will accrue. At the end of the trial, if at least 4 out of the 19 patients achieve an objective recovery at 100 days, the boost intervention will be considered promising for further investigation. The type I and type II errors are both set at 0.10.

The estimated accrual is 4-5 patients/year and the overall study duration is 4-5 years.

Amended: 02-DEC-2015

Page 17 of 24

The Cohort B trial includes early termination in the event that patients have high rates of grade III-IV acute GVHD. The stopping rules below are based on a maximum of 19 patients receiving the boost intervention.

Failure Type	# of failures needed to stop the study	Failure rate in the population	Probability boundary is crossed
Acute GVHD (Grade III-IV)	2 in the first 4 patients	0.10	0.10
	3 in the first 8 patients		
	4 in the first 14 patients		
	5 at any point	0.35	0.89

This trial includes a number of secondary objectives that will be explored separately for the two cohorts.

1. The objective count recovery will be tabulated by the severity of PGF at the time of the boost.
2. Overall survival following the TCD boost will be estimated using Kaplan-Meier methodology.
3. The incidence of grade II-IV and III-IV acute GVHD and chronic GVHD will be estimated using cumulative incidence functions. Competing risks for these events include relapse and non-relapse mortality.
4. The frequency of serious infections as defined by CIBMTR will be tabulated for the two patient cohorts.
5. The levels of T-cell chimerism will be compared for patients who do and who do not achieve the 100-day objective count recovery endpoint.
6. Immune reconstitution will be explored using graphical and descriptive measures.

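### Could a recovery that follows a second boost or transplant before day 100 be credited to the study boost?

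*Combined protocol and SAP*

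**What the plan says.** Section 14.0 defines the primary endpoint in both cohorts as "achievement of objective count recovery as defined in section 12.0 at 100 days following the intervention without the aid of growth factors". It then scores as treatment failures "Patients who die prior to 100 days or those who achieve count recovery but lose their counts prior to 100 days". Item 1 of Section 12.0 sets the count thresholds and requires that they hold "without support of blood product transfusions and/or growth factors".

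The final rules are fixed counts. Cohort A is promising "if at least 15 out of the 28 patients achieve an objective recovery at 100 days", and Cohort B "if at least 4 out of the 19 patients achieve an objective recovery at 100 days".

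On repeat treatment, item 4 of Section 6.2 reads: "Patient who underwent TCD boost without counts recovery and are considered for another TCD boost will be treated off protocol". Section 13.0 covers removal, which applies "If at any time the patient is found to be ineligible for the protocol" or at the patient's request. It does not list further donor cells as a reason. The GVHD stopping rules in Section 14.0 describe the 28 and the 19 as patients who receive the boost.

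**The concern.** The endpoint lists what disqualifies a recovery (transfusion, growth factors) and what counts as failure (death, loss of counts). Further donor cells are in neither list. On a strictly literal reading, a boosted patient who has a second boost or a second transplant within the window and meets the counts unsupported at day 100 satisfies the definition and is in neither failure category.

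The event is foreseeable. Section 3.1 names a second transplant or more stem cells as the options when low counts persist. Section 6.2 does not settle the scoring: its list concerns status at enrolment, the item covers only another T-cell depleted boost, and it is about treatment.

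At stake is the false-positive rate. Compared with a rule that scores such patients as failures, counting them as successes can only add responders. The decisions turn on one patient: 14 or 15 of 28, and 3 or 4 of 19. A related question is whether patients removed under Section 13.0 stay in the 28 and 19.

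**Working it through.** **Inputs (Section 14.0).** Cohort A: null rate p0 = 0.40, target p1 = 0.65, 13 patients in stage 1, stop at 5 or fewer, success at 15 or more of 28. Cohort B: p0 = 0.10, p1 = 0.35, 11 patients in stage 1, stop at 1 or fewer, success at 4 or more of 19. Both error limits are 0.10.

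**Step 1: reproduce the designs.** The probability of a promising verdict at true rate p is the sum, over stage 1 counts x above the stopping limit, of P(X1 = x) × P(X2 ≥ r − x). X1 and X2 are binomial with the stage sizes, and r is 15 or 4.

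| | Type I error at p0 | Power at p1 |
|---|---|---|
| Cohort A | 0.0930 | 0.9035 |
| Cohort B | 0.0988 | 0.9086 |

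A full search for the optimal design under the same limits returns these two designs. No stated figure is in dispute.

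**Step 2: size the effect if such recoveries were counted.** The documents give no rate for further donor cells before day 100, so the inputs here are assumptions. Let g be the share of non-responders who receive further cells. Suppose they recover in time at half the null rate, since less of the window remains. The share of non-responders converted is s = g × p0/2, and the rate under the null becomes p = p0 + (1 − p0)s.

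| g | A: s | A: p | A: type I error | B: s | B: p | B: type I error |
|---|---|---|---|---|---|---|
| 2% | 0.004 | 0.4024 | 0.097 | 0.001 | 0.1009 | 0.101 |
| 5% | 0.010 | 0.4060 | 0.104 | 0.0025 | 0.10225 | 0.105 |
| 10% | 0.020 | 0.4120 | 0.117 | 0.005 | 0.1045 | 0.112 |

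**Step 3: what larger figures would require.** Setting s directly at 1% or 2% gives 0.125 or 0.155 in Cohort B. Under the same model, g = s/(p0/2) = 0.01/0.05 = 20% or 0.02/0.05 = 40%. Those values therefore need a fifth to two fifths of Cohort B non-responders to receive further cells in time. Even then the expected number of converted patients at full accrual is small: 19 × 0.90 × 0.01 = 0.17, or 0.34 at 2%.

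**Step 4: is the event likely within the window?** In the retrospective series of Section 3.3, improvement "occurred in 20 patients with a median of 3.4 months" after the boost. That is about 3.4 × 30.4 = 103 days, already past day 100, and on a lower neutrophil threshold than the trial's (0.5 against 1.0 × 10⁹/L). A second product would first have to be given after the study boost had been judged to fail, and then produce stable unsupported counts in the time left. Some non-responders could never receive it: 7 of the 35 patients in that series (20%) died within 28 days. The range for improvement starts at 0.36 months (about 11 days), so the event is possible. Section 3.3 reports no such case.

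**Step 5: read the sections together.** Section 14.0 measures recovery following the intervention, which Section 4.2 identifies as the study boost. Section 6.2 treats a patient considered for another boost as one whose counts did not recover, and puts that treatment outside the protocol. Together they point to non-response to the study boost.

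**The case for a change.** The strongest reply is that intent is not a rule. Section 6.2 is headed by status at enrolment and says nothing about a second transplant or an unmanipulated product, and the failure list in Section 14.0 could have named further cells. Cohort B is sensitive because its null is only 10%: the chance under the null of ending exactly one responder short is 0.112, against 0.065 in Cohort A. A scoring sentence would cost no patients and no visits.

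What stands is that the text is silent and that one patient could in principle decide a cohort. What does not stand is that the plan scores such a patient as a success: silence is not a scoring rule, and the surrounding text points the other way. The one-short probabilities show how often a single patient would matter. They are not error rates and do not make the event more common. The inflation in Step 2 also presumes that the null rates exclude such recoveries. Cohort A's benchmark comes from institutional history, and Section 3.3 does not say how further cells were scored there. If they were counted, the null already contains them.

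On the denominator, the GVHD rules already describe the same 28 and 19 as boost recipients. What remains open is whether patients removed later stay in the count, and an analyst would keep them.

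**Conclusion.** No change to the plan is needed. This is missing detail that analysts would fill sensibly: further donor cells before day 100 scored as non-response to the study boost, boosted patients kept in the 28 and 19, and a missing day-100 count treated as non-response. No stated number or rule is wrong, and both designs hold their 0.10 error limits.

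Even if such recoveries were counted, type I error would be at most 0.117 (Cohort A) and 0.112 (Cohort B) with up to 10% of non-responders receiving further cells. That rests on two assumptions the documents cannot confirm: the share who receive further cells, and recovery at half the null rate. Heavy early use of further cells would be needed for a material effect, and nothing in the documents suggests it.

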#### Cohort A:

A Simon's 2-stage optimal design will be used to investigate the primary endpoint in patients without active infection or end organ disease. Based on historical MSKCC data, the boost treatment strategy will be considered promising for further investigation if 65% achieve objective recovery at 100 days.

However, if 40% or fewer achieve sustained recovery, the strategy will not be considered.

promising. Based on these rates, the trial will accrue a maximum of 28 patients. In the first stage of the trial, response will be evaluated in the first 13 patients. The trial will stop due to a lack of efficacy if 5 or fewer achieve objective recovery; otherwise, an additional 15 will accrue. At the end of the trial, if at least 15 out of the 28 patients achieve an objective recovery at 100 days, the boost intervention will be considered promising for further investigation. The type I and type II errors are both set at 0.10.

The estimated accrual is 7-10 patients/year and the overall study duration is 3-4 years.

The Cohort A trial includes early termination in the event that patients have high rates of grade III-IV acute GVHD. The stopping rules below are based on a maximum of 28 patients receiving the boost intervention.

Failure Type	# of failures needed to stop the study	Failure rate in the population	Probability boundary is crossed
Acute GVHD (Grade III-IV)	3 in the first 8 patients	0.10	0.09
	4 in the first 14 patients 5 in the first 20 patients 6 in the first 27 patients 7 at any point		
		0.35	0.96

